10. POTENTIAL BENEFITS TO SUBJECTS

Subjects' lower limb swelling (edema) and associated symptoms (e.g., pain, discomfort, heaviness) may decrease with use of the TENS device. All subjects will receive the TENS device with the commercially-available stimulation settings (list price \$299) to keep at the end of the study. However, they will have to purchase electrodes for continued use of the device (list price \$29.95/~4 weeks of use).

11. COSTS FOR PARTICIPATION

If the subject does not have a monthly data plan, they may incur some minimal data usage costs when connecting to the Quell App.

Other than the above-described costs the subjects and insurance companies will not be responsible for any study-related costs. However, if a subject requires medical attention as a result of being in the study (e.g., requires a cream for skin irritation), the subject will be responsible for the costs of those interventions.

12. PAYMENT FOR PARTICIPATION

Subjects will be paid \$75 total for taking part in this study. The payment of \$75 will be initiated at in-person Visit 3. For this study we will use a subject payment system called Advarra Participant Payments. The system allows three ways to provide payment. Subjects can choose: a reloadable debit card; direct deposit; or mailed paper checks. The study team will help create a "subject profile" in the system. In order to provide payment, the subject will need to enter their name and date of birth into their subject profile. Depending on which payment method they choose, they may also need to enter their email address and banking information. If the subject already has an Advarra account (because of another study that uses this system), the existing profile will be used to provide payment.

Payment received for participation in research is considered taxable income. If subjects receive \$600.00 or more in any one calendar year from UR or its affiliates, the University is required to report this information to the Internal Revenue Service (IRS) in a 1099 (Miscellaneous Income) form. They will be sent a copy of this form and a copy will be sent

Page 20 of 26

to the IRS. Depending on the amount they are paid, they may be asked to submit a W-9 form, which includes their Social Security Number.

.

13. SUBJECT WITHDRAWALS

Subjects will be withdrawn if they become pregnant during the study because pregnancy can cause edema and change the study outcome. The PI can withdraw any subject who is at risk or is unable to participate further due to new identification of conditions that are contraindicated with use of TENS (e.g., epilepsy). Data that have already been collected will be included in the analyses.

The subject may be withdrawn from the study if they do not keep appointments for study visits, specifically in the beginning of the study.

If the subject misses the baseline period visit and does not attend rescheduled visits with in the 7-day grace period they will be withdrawn from the study prior to registration or distribution of the treatment device.

The subject may be withdrawn from the study if they cannot complete study activities.

If the subject's baseline daily diary entries have more than 4 days or greater missing they will be withdrawn from the study before registration or distribution of the treatment device.

If subjects withdraw from the study, reasons for withdrawal will be documented and data collected up until the point of withdrawal will be included in the analyses unless the subject indicates that they do not want their previously collected data used. Subjects will be allowed to refuse any study activity and can still remain in the study if they are willing. Subjects who withdraw from the study will not be replaced.

14. PRIVACY AND CONFIDENTIALITY OF SUBJECTS AND RESEARCH DATA

Research staff members will only approach subjects after introduction by a clinician either inperson or via MyChart, phone call, or signed letter. While on the study, subjects will not be contacted via phone, email or, video call more frequently or for reasons other than those stated in the protocol.

Only study personnel, including the principal investigators, co-investigators, and research staff will have access to the study data. The Quell (i.e., TENS device) App will be setup using a deidentified study email so that the data collected via the application will not be identifiable by anyone outside of the study team. Paper data forms will be locked in a secure office and electronic data will be stored on a password protected, encrypted network drive. Each subject will receive a unique ID number. Data will be entered electronically via the

University of Rochester's secure REDCap system or directly into excel on a University of Rochester computer. A master key that links the study ID numbers with the subjects will be kept in a separate file, also on a University of Rochester secured network drive.

Page 21 of 26

The Fitbit (i.e., Fitbit device) account registration will be setup using a de-identified study email and password combination for each subject, so that the data collected via the Fitbit device and secure cloud database will not be identifiable by anyone outside of the study team. The account will use a de-identified placeholder for the first and last name. Demographic details such as weight, height and DOB are collected to ensure accurate data capture. The subject's device account settings will be set to the highest privacy-protection options available for the device interface. At Visit 3 the coordinator will deactivate and deregister the Fitbit, which will delete the de-identified data from the device immediately and from the Fitbit secure cloud database within 90 days.

The fact that the subject is enrolled in the research study will be indicated in their electronic medical record. The eRecord note will indicate that the subject will be using a TENS device for their peripheral edema for 3 weeks during the study and that providers can contact the PI for questions regarding the subject's participation in the study.

15. DATA AND SAFETY MONITORING PLAN

Adverse Event (AE) Definition

An adverse event (AE) is any symptom, sign, illness, or experience, which develops or worsens during the course of the study, whether or not the event is considered related to study intervention (Table 4).

Table 4. Attribution. Categories to define the relationship between the adverse event and study device/intervention.

| ATTRIBUTION | DESCRIPTION |
|-------------|---|
| Unrelated | The AE is clearly NOT related to the study device /intervention |
| Unlikely | The AE is doubtfully related to study device /intervention |
| Possible | The AE may be related to study device/intervention |
| Probable | The AE is likely related to study device/intervention |
| Definite | The AE is clearly related to study device/intervention |

Serious Adverse Event

A serious AE is defined as any adverse medical experience that results in any of the following outcomes:

- death:
- is life-threatening;
- requires inpatient hospitalization or prolongation of existing hospitalization;
- results in persistent or significant disability/incapacity;
- is a congenital anomaly/birth defect; or
- requires medical or surgical intervention to prevent permanent impairment or damage.

Page 22 of 26

Recording Adverse Events

AEs will be assessed by phone after 1 week of the intervention is started, at the 3rd in-person study visit. The study staff will assess adverse events by asking subjects if they have experienced any new symptoms since starting the experimental treatment. They will ask specifically if any skin reactions have occurred.

AEs will be recorded in the **AE form**, including the date of onset, date of resolution, description of the AE, severity, whether or not the AE is considered serious, any action taken to treat the AE, likelihood that the AE is related to the experimental device, any change to the experimental device usage in response to the AE, and whether the RSRB was notified regarding the AE. Any AEs will be followed up as clinically appropriate by the Co-I /medical monitor (MM). Table 5 indicates the types of AEs (i.e., by severity level / attribution category) that will be recorded and reported to the RSRB during annual reviews.

Table 5. Reportable adverse events

| Adverse Even | t | | | | |
|--------------|----------|----------|----------|----------|----------|
| Attribution | Grade 1 | Grade 2 | Grade 3 | Grade 4 | Grade 5 |
| Unrelated | | | recorded | recorded | recorded |
| Unlikely | | | recorded | recorded | recorded |
| Possible | recorded | recorded | recorded | recorded | recorded |
| Probable | recorded | recorded | recorded | recorded | recorded |
| Definite | recorded | recorded | recorded | recorded | recorded |

Responsibilities for Reporting Serious Adverse Events

All serious AEs will be recorded in the AE form. Serious AEs will be reported to the RSRB if they are considered unanticipated and related to use of the TENS device or involves increased risk to subjects or others than was previously known or expected. If an AE is reportable, it will be reported to the RSRB using the "Reportable Event" form in the online IRB click system within 10 calendar days of the investigator or research staff member's learning of the event.

Data Monitoring

The study team will review the data and patient safety after the first five subjects are enrolled and then every 6 months. Subject enrollment will not be paused during these reviews. The PI will submit annual progress reports of these data to the Safety Monitor ([name]). [name] is a neurologist who is familiar with the TENS device from a previous study of the device used by subjects with chemotherapy-induced peripheral neuropathy. The reports will include: the number of patients enrolled, and for each treatment: withdrawals, AEs possibly, probably, or definitely associated with the therapy, all serious AEs both expected and unexpected, dose adjustments, and responses observed. The PI will maintain a database of all

Page 23 of 26

AEs with toxicity grade and information regarding treatment-required complications, or sequelae.

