9. RISKS TO SUBJECTS

Potential risks from stopping use of compression stockings or wraps: If subjects choose to forgo use of compression stockings or wraps to start the trial, there is a risk that their edema could worsen during the study. We have minimized this risk by only enrolling subjects who are not experiencing a significant of benefit from these therapies (i.e., entry criteria: "based on shared decision making of the potential subjects' clinician or the clinician co-investigator [the potential subject is] receiving sufficiently little benefit from these therapies to warrant stopping their use for the duration of the study"). Subjects will be asked to call the study staff if they feel as though their swelling or symptoms are worsening and they will decide together with the clinician Co-I if they should stop using the TENS device and resume using compression stockings or wraps.

Potential risk of not trying currently available treatment options: For some people, the following treatments can be tried for peripheral edema, (1) compression stockings, (2) Velcro wraps, (3) manual lymphatic drainage, (4) short stretch bandage wrapping, (5) pneumatic pumps, (6) kinesiotape, (7) acupuncture, and (8) cupping. For potential subjects who have not been offered these treatments in the past, choosing to join the study and forgoing these treatments could lead to a worse outcome than if they tried one of these alternative treatments. The potential subjects will be informed of these alternative treatment options and given the opportunity to consult their primary care physician or the clinician Co-I regarding whether they should consider the alternative treatments prior to starting the study.

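### Non-serious edema worsening put down to stopping compression has no attribution category, and if rated Unrelated or Unlikely it can go unrecorded at Grade 1-2 and is absent from the Safety Monitor's AE listing at any grade

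*Combined protocol and SAP*

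**What the plan says.** Section 9 (Risks to Subjects) opens with the consequence of giving up compression stockings or wraps to enter the trial: "there is a risk that their edema could worsen during the study". Inclusion criterion 6 in Section 5 admits subjects by that route when a clinician agrees that the benefit is too small to justify continuing.

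Section 15 defines an adverse event as one "which develops or worsens during the course of the study, whether or not the event is considered related to study intervention". Four later provisions of that section decide what happens to the event:

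- Table 4 sets out "Categories to define the relationship between the adverse event and study device/intervention". Section 4.2, which describes the study intervention, covers only the TENS device.
- The AE form records the "likelihood that the AE is related to the experimental device".
- On scope, "Table 5 indicates the types of AEs (i.e., by severity level / attribution category) that will be recorded", and the same types go to the RSRB at annual review. The Unrelated and Unlikely rows are empty at Grades 1 and 2. Every other cell is marked as recorded.
- The annual report to the Safety Monitor lists "AEs possibly, probably, or definitely associated with the therapy, all serious AEs both expected and unexpected", together with withdrawals and observed responses.

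Section 15 also says that all serious AEs go on the AE form, and that the principal investigator keeps a database of all AEs with toxicity grade.

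**The concern.** The plan names a harm that comes from taking part rather than from the device, then builds its attribution scale and AE form around the device. A coordinator who believes that a subject's legs swelled because the stockings came off has no field in which to say so. Read literally, the form steers that judgment towards Unrelated or Unlikely, and for mild and moderate non-serious events those ratings decide whether any AE record exists.

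Two things are at stake. First, the Safety Monitor, who sees an annual summary, would not see these events in the AE listing. Second, the pilot is meant to inform a later trial, and the record of what happened to subjects who stopped compression would be incomplete as safety data. With one open-label arm there is no comparator, so relatedness is purely a judgment and a weak basis for deciding whether a mild event is written down.

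**Working it through.** The plan gives no event rate or numerical target here. The check traces one event through the rules and counts the cells of Table 5.

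**Step 1: attribution options.** Table 4 refers to the study device/intervention, Section 4.2 identifies that as TENS, and the AE form names the experimental device. No category covers study procedures or the withdrawal of earlier therapy.

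**Step 2: cells in Table 5.** 5 attribution rows x 5 grades = 25 cells. Blank cells: 2 rows (Unrelated, Unlikely) x 2 grades (1, 2) = 4. Recorded cells: 25 - 4 = 21. Within Grades 1-2 alone there are 5 x 2 = 10 cells, of which 4 are blank.

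**Step 3: path of an edema worsening that staff ascribe to stopping compression.**

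| Rating and grade | Recorded under Section 15 | Annual RSRB review | Safety Monitor's AE listing |
|---|---|---|---|
| Unrelated/Unlikely, Grade 1-2, non-serious | No | No | No |
| Unrelated/Unlikely, Grade 3 or higher, non-serious | Yes | Yes | No |
| Any rating, serious | Yes | See note | Yes |
| Possible or higher, any grade | Yes | Yes | Yes |

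Note: serious events are recorded whatever the rating, and annual review follows Table 5. Prompt RSRB reporting of a serious event depends on separate criteria: unanticipated and TENS-related, or a risk greater than previously known.

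**Step 4: consistency within Section 15.** The definition counts an event "whether or not the event is considered related to study intervention". The database is to hold all AEs. Table 5 leaves four combinations of grade and attribution unrecorded. These three statements cannot all be followed.

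**Step 5: elicitation.** At Phone Call 1 (Section 8), and in the recording rules of Section 15, staff ask about new symptoms. Section 15 adds a specific question on skin reactions only. Every subject enters with pitting edema of at least 2+ (inclusion criterion 2), so a worsening is not obviously a new symptom. Section 9 asks subjects to call if swelling worsens, but does not say that the call produces an AE record.

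**Step 6: can the loss be counted?** Expected unrecorded events = 52 x s x w x g x u, where s is the share who stop compression to enter, w the share of those who worsen non-seriously, g the share of worsenings at Grade 1-2, and u the share of these rated Unrelated or Unlikely. The documents give only the 52. The toxicity grading scale is also undefined, so g could not be worked out even if s and w were known. The product is 0 if u = 0 and has no documented upper value below 52 x s x w. No count is therefore offered.

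**The case against.** The strongest reply is that the plan captures most of what matters. Table 5 records Grades 3-5 at every attribution and sends them to annual RSRB review. All serious AEs are recorded and reach the Safety Monitor. A reader might infer that edema worsening from stopping compression disappears from AE records and safety reports altogether. The documents do not support that, and this part of the reply stands.

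A reader might also infer that such worsening must be rated unrelated. No rule says so. Unrelated requires a clear absence of relation, whereas Possible needs only that "The AE may be related to study device/intervention". With the device worn on the leg and no control arm, staff may often be unable to rule it out, and Possible brings the event back at every grade. This also stands, but it leaves capture to individual judgment, and the form's device-only wording invites a lower rating from anyone convinced that compression is the cause.

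Third, swelling is measured as an outcome, by volumeter, tape and diary. The study team reviews data and safety after five subjects and then every 6 months, and the Safety Monitor also receives withdrawals and observed responses. So it would be wrong to say that worsening is invisible or that its extent cannot be studied. These sources do not assign a cause, however, and are not event-level safety reports.

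Finally, Section 16 plans no analysis of AE rates, so a claim of bias in a planned AE estimate would have no target. That is correct. The gap lies in recording and reporting.

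**Conclusion.** The point holds for non-serious events only. If edema worsening is ascribed to stopping compression or wraps and rated Unrelated or Unlikely, it is unrecorded under Table 5 at Grade 1-2, and at any non-serious grade it is absent from the Safety Monitor's AE listing. The blank cells also contradict the AE definition and the all-AE database, and that contradiction needs no assumption about how staff rate events.

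In size, 4 of 25 cells are affected, and the number of events behind them is unknown. The conclusion assumes that staff read the intervention as TENS, as Section 4.2 and the AE form imply, and that some worsenings are rated below Possible. It does not require that all are. The matter deserves correction because the risk is one the protocol itself names and the change is small.

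**What to change.** 1. In Table 4 and on the AE form, rate each event twice: against (a) the TENS device and (b) other study requirements, including stopping compression or wraps.
2. In Table 5 and in the Safety Monitor report, treat Possible or higher on either rating as related.
3. Reconcile Table 5 with the AE definition and the all-AE database by recording Grade 1-2 worsening of lower-limb swelling, new limb sensations and skin events regardless of attribution.
4. Reword the existing AE question to ask about new or worsened symptoms. Without this, an extra attribution field cannot capture worsening that nobody asked about.

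The cost is one added form field and some wording in Tables 4 and 5, the AE question and the report specification. A few more mild AEs will be logged, some overlapping with the swelling outcome, and the AE count will look less favourable. The change does not extend AE monitoring to the pre-baseline week, for which Table 2 marks none.

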Visit 2- Baseline visit: (In-person / Day 0 up to + 5_days)

The coordinator will download the Quell App to the subject's mobile device, setup a Quell Health account for the subject (using valid de-identified study email address and password) and help them pair the TENS device to their mobile device and calibrate it. They will introduce the concept of TENS and describe how it is likely to feel to the subjects using a standardized script. They will give the subject 2 electrode strips along with the TENS device, which should be sufficient for the 3-week duration of the treatment period of the study. They will provide the subject with the subject guide to help them with at-home use and ask them to use the device between 7 to 8 hours per day. They will also ask them to open the Quell App once a day while the device is connected to cellular data or Wi-Fi to transfer the data to the Quell Health account. If the subject plans to use cellular data, the coordinator will setup the Quell App to allow the use of cellular data in the settings.

The coordinator will review the Edema Symptom Daily Diary, Edema Symptom Inventory Week Recall, and Edema Symptom Inventory-Week Recall 0-10 Scale forms and teach the subject how to complete them.

The coordinator will perform the ankle range of motion and lower limb sensation tests and measure the subject's lower limbs using the volumeter and tape measure.

The subject will complete the visit related patient-reported outcome measures (PROs) at the study visit if they were not completed previously using the REDCap link.

Weeks 1-3: (subject will do at home)

- Subject will use the Fitbit Device at all times.
- Subject will use the TENS device for 7 to 8 hours / day either day, night, or asleep.
- Subject will complete the Edema Symptom Daily Diary, Edema Symptom Inventory Week Recall, and Edema Symptom Inventory-Week Recall 0-10 Scale.

Phone Call 1: (Day 7, up to +2 days)

- AE assessment: The coordinator will ask the subject using an open-ended question whether any new symptoms have occurred since starting the study. If so, the coordinator will record the AE in the **AE form** in REDCap.
- Adherence discussion: The coordinator will discuss any adherence problems observed in the data from the Quell App.
- Reminder 3: remind the subject (and record in the **Telephone Contact Form**):
- To complete at-home (paper) PROs for Week 2 (Days 7-14).

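### Section 15 can be read in two ways on whether non-serious grade 1–2 adverse events rated unrelated or unlikely are recorded at all

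*Combined protocol and SAP*

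**What the plan says.** Several places bear on which AEs enter the data.

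- **Section 15, AE definition.** An event counts as an AE "whether or not the event is considered related to study intervention".
- **Section 8, Phone Call 1.** The coordinator asks an open question about "whether any new symptoms have occurred since starting the study. If so, the coordinator will record the AE in the" AE form. No grade or attribution condition is attached.
- **Section 15, Recording Adverse Events.** AEs go on the AE form. Its fields include severity, "likelihood that the AE is related to the experimental device", and whether the RSRB was told of the event.
- **Section 15, Data Monitoring.** "The PI will maintain a database of all" "AEs with toxicity grade and information regarding treatment-required complications, or sequelae" (one sentence, split by a page break).
- **Section 15, Table 5.** The lead-in describes the AE types "that will be recorded and reported to the RSRB during annual reviews". The row for the second attribution category reads "Unlikely | | | recorded | recorded | recorded", so grades 1 and 2 are empty. The Unrelated row has the same pattern. The table's title speaks of reportable events.
- **Section 15, serious AEs.** A separate sentence puts every serious AE on the AE form, with no exception for grade or attribution.

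**The concern.** The first four items describe a system in which everything elicited is written down and attribution is one of the things written. Table 5 sits in the subsection on recording, and both its lead-in and its cells use the word *recorded*. A coordinator could therefore take it as the rule for what to enter. On that reading, someone decides whether an event is unrelated or unlikely before anything is written, and an event so rated at grade 1 or 2 leaves no AE form.

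This matters because the study has one arm and no control rate. A mistaken relatedness call cannot be corrected later by comparing groups; it can only be found by going back to the individual events. Section 9 reports new abnormal foot sensations with the device in a previous pilot. Section 4 collects history of diabetes and peripheral neuropathy, and Section 5 excludes neither, so in some subjects the attribution of a mild new foot sensation could be open to argument. At stake is whether such events remain available for a second look, and whether an AE count from this study has one meaning.

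**Working it through.** No AE figure in the plan can be reproduced, so the check is mainly a comparison of texts.

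**1. What Table 5 leaves out.** Five attribution categories by five grades give 25 cells. Unrelated and Unlikely each have 3 filled cells; Possible, Probable and Definite each have 5. Filled: 2 × 3 + 3 × 5 = 21. Blank: 25 − 21 = 4, namely grades 1 and 2 in the first two rows. The same gap appears in both rows, and the lead-in itself says *recorded*, so this does not look like a fault of text extraction.

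**2. One test case under each rule.** Take a non-serious grade 1 symptom mentioned at Phone Call 1 and judged unlikely to be related.

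| Rule | On the AE form? |
|---|---|
| Phone Call 1 (Section 8) | Yes |
| AE form paragraph (Section 15) | Yes, with attribution as a field |
| Database of all AEs (Section 15) | Yes |
| Table 5 read as a reporting filter | Yes, but not in the annual RSRB report |
| Table 5 read as a recording filter | No |

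Only the last reading conflicts with the rest. No text says which reading governs.

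**3. The same case, but serious.** The explicit sentence on serious AEs puts it on the form under every reading. The affected set is therefore the non-serious events in the four blank cells.

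**4. Who else would see these events.** The annual report to the Safety Monitor covers AEs rated possibly, probably or definitely related, plus all serious AEs. Events in the affected set reach neither that report nor, under either reading of Table 5, the annual RSRB report. The AE form and the PI's database are the only places Section 15 provides for them. If Table 5 filters recording, they are missing there too.

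**5. Size.** Let N be the number of AEs elicited and q the share that are non-serious and fall in the four blank cells. Recording everything gives N events; using Table 5 as a recording filter gives N × (1 − q). The relative loss is q by construction. The documents give neither N nor q, so as far as they show, q could lie anywhere from 0 to 1. Putting in assumed values would only return the assumption.

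**6. Link to planned analyses.** Section 16 specifies no AE rate or other safety analysis, and neither the aims in Section 1 nor the feasibility outcomes in Section 4 include tolerability. No planned test or estimate changes.

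**The case against.** The strongest reply is that the passages already fit together. Table 5 is titled as a list of reportable events, and its lead-in ends with annual RSRB review. Read that way it filters reporting only. The form has a field for whether the RSRB was notified, which suggests that forms also exist for events that are not reported. This stands as far as it goes: a coherent reading exists, and it is probably the sensible one. It does not settle the matter, because the lead-in joins recording and reporting, every filled cell says *recorded*, and staff are not told which reading to use.

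A reader might infer more than the documents support:

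- **That attribution is decided before recording.** This follows only if Table 5 is used as an entry filter. The AE form paragraph makes attribution a field filled in when the event is recorded.
- **That mild serious events could be lost.** The explicit serious-AE sentence prevents this; a blank table cell does not override it.
- **That a planned AE rate is biased.** Section 16 plans none. The effect is on any count reported later.
- **That the device's known harms would disappear.** Section 9 links skin irritation and abnormal foot sensations to the device and tells subjects to call the team about new abnormal sensations. Section 15 has staff ask specifically about skin reactions. Many such events would probably be rated possible or higher and so be recorded at any grade. Some foot sensations in subjects with neuropathy remain debatable, but nothing in the documents says how many.

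**Conclusion.** The ambiguity is in the current text and should be removed. Three unfiltered instructions stand against a table that, by its lead-in and cells, can be taken to leave out non-serious grade 1–2 events rated unrelated or unlikely. The consequence is conditional: if staff apply Table 5 as a recording filter, those events leave no AE form to re-review, and any AE count from this single-arm study depends on which rule was followed. If they treat it as a reporting list, nothing is lost.

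The size cannot be estimated from the documents. Serious AEs and the planned analyses are untouched. Counts of events rated possible or higher are affected only where an event that should have been rated so was judged unrelated or unlikely. This is a cheap improvement to safety capture, not evidence of a large error. It is still worth making before enrolment is complete, because an event that was never written down may not be recoverable.

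**What to change.** In Section 15, under Recording Adverse Events, state that every AE of any grade and any attribution is entered on the AE form with its grade and attribution. Then reword Table 5 and its lead-in so that the table defines only the subset sent to the RSRB at annual review, with *reported* replacing *recorded* in the cells. Phone Call 1, the AE form paragraph and the PI's database then agree with the table, and the serious-AE sentence can stay as it is.

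The cost is a short text change and a few more AE form entries in a study of 52 subjects with 3 weeks of treatment and two scheduled AE contacts (Phone Call 1 and Visit 3). How AEs should be summarised is a separate question and need not be settled to make this correction.
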